#### **7.4 Dosage Modification**

No reductions or modifications of the assigned dose are allowed. If the infusion is interrupted for any reason, the infusion may be restarted at the discretion of the investigator. If an incomplete dose is administered at any visit, the participant will resume the assigned dose/administration schedule at the next visit. See [Section 9.2.9](#) for management of IRRs.

#### **7.5 Preparation/Handling/Storage/Accountability**

The IP should be stored in a secure area according to local regulations. It is the responsibility of the investigator to ensure that IP is only dispensed to study participants. The IP must be dispensed only from official study sites by authorized personnel according to local regulations.

The product storage manager should ensure that the study treatment is stored in accordance with the environmental conditions (temperature, light, and humidity) as determined by BMS. If concerns regarding the quality or appearance of the study treatment arise, the study treatment should not be dispensed and BMS contacted immediately.

Please refer to the Pharmacy Manual for IP preparation.

Study treatment not supplied by BMS will be stored in accordance with the package insert.

The IP documentation (whether supplied by BMS or not) must be maintained that includes all processes required to ensure drug is accurately administered. This includes documentation of drug storage, administration, and, as applicable, storage temperatures, reconstitution, and use of required processes (eg, required diluents, administration sets).

Further guidance and information for final disposition of unused study treatment are provided in [APPENDIX 2](#).

### **7.5.1      *Retained Samples for Bioavailability/Bioequivalence/Biocomparability***

Not applicable.

### **7.6      *Treatment Compliance***

Not applicable.

### **7.7      *Concomitant Therapy***

All medications taken from 4 weeks prior to the screening visit until the last study visit must be recorded on the eCRF. Prior medications are defined as medications taken within 4 weeks of the screening visit. Concomitant medications are defined as any medication taken after the first dose of study medication until the last study visit. Concomitant medications (prescription, OTC, or herbal) should be administered during the study only if they are prescribed for treatment of specific clinical events.

Participants taking vitamin E, SGLT2 inhibitors, GLP-1 receptor agonists, anti-obesity agents, or an approved NASH treatment at stable doses prior to screening (as specified in [Section 6.1](#)) should maintain stable dosing throughout the entire study. In certain circumstances, dose modifications of concomitant medications may be made based upon the investigator's clinical judgement, after consultation with the Medical Monitor.

SARS-CoV-2 vaccines approved for Emergency Use Authorization by local regulatory agency that are not live attenuated are allowed during the study and should be handled in the same manner as other vaccines.

#### **7.7.1      *Prohibited and/or Restricted Treatments***

Restrictions and prohibitions on prior and concomitant medications and/or treatments are as follows:

- 1) Prior exposure to BMS-986263 is prohibited.
- 2) NASH therapies with only accelerated approval from the US FDA or conditional approval from the European Medicines Agency are prohibited from the time of the liver biopsy to confirm eligibility until Week 12 or early termination.
- 3) OTC herbal supplements or multivitamins containing vitamin A (including Cod liver oil), or other medications that may contain vitamin A are prohibited after signing the ICF and throughout the study.
- 4) Other investigational agents. Any other investigational agent must be discontinued at least 3 months prior to the liver biopsy used to confirm eligibility or within 12 weeks or 5 half-lives prior to the first dose of study treatment, whichever is longer.
- 5) Medical or surgical treatments for obesity should not be initiated while the participant is participating in the study.
- 6) Concomitant use of nintedanib is prohibited. Prior use of nintedanib is permitted but must be discontinued at least 3 days before the first dose of study treatment.

- 7) Participation in other interventional clinical trials.
- 8) Use of anticoagulants is prohibited after signing the ICF and throughout the study, unless needed in the opinion of the investigator for safety reasons after Randomization.

## **7.8 Treatment After the End of the Study**

At the end of the study, BMS will not continue to provide BMS-supplied study treatment to participants/investigators unless BMS chooses to extend the study. The investigator should ensure that each participant receives appropriate standard of care to treat the condition under study.

BMS reserves the right to terminate access to BMS-supplied study treatment if any of the following occur: a) the study is terminated due to safety concerns or other reasons; b) the development of BMS-986263 is terminated for any reason, including but not limited to lack of efficacy and/or not meeting the study objectives; c) the participant can obtain medication from a government-sponsored or private health program. In all cases BMS will follow local regulations.

## **8 DISCONTINUATION CRITERIA**

### **8.1 Discontinuation from Study Treatment**

Participants MUST discontinue IP (and non-IP at the discretion of the investigator) for any of the following reasons:

- Participant's request to stop study treatment. Participants who request to discontinue study treatment will remain in the study and must continue to be followed for protocol-specified follow-up procedures. The only exception to this is when a participant specifically withdraws consent for any further contact with him/her or persons previously authorized by participant to provide this information.
- Any clinical AE, laboratory abnormality, or intercurrent illness which, in the opinion of the investigator, indicates that continued participation in the study is not in the best interest of the participant.
- Termination of the study and/or program by BMS.
- Loss of ability to freely provide consent through imprisonment or involuntarily incarceration for treatment of either a psychiatric or physical (eg, infectious disease) illness.
- Symptoms, physical exam findings, or laboratory abnormalities consistent with [REDACTED] that, at the discretion of the investigator, cannot be explained by another cause.

- For participants with normal Day 1 (Randomization) liver enzymes, total bilirubin, and INR, if there is new elevation of ALT or AST  $> 3 \times$  ULN, repeat testing should be performed within 48 hours to 72 hours. If elevation persists, then DILI discontinuation criteria will be applied and study treatment will be discontinued if any of the following occur:

- ALT or AST  $> 8 \times$  ULN
- ALT or AST  $> 5 \times$  ULN for more than 2 weeks
- ALT or AST  $> 3 \times$  ULN and (total bilirubin  $> 2 \times$  ULN or INR  $> 1.5$ )
- ALT or AST  $> 3 \times$  ULN with the appearance of fatigue, nausea, vomiting, right upper quadrant pain or tenderness, fever, rash, and/or eosinophilia ( $> 5\%$ )

*Note: If necessary, a local laboratory may be used for repeat testing, and results should be promptly communicated to the site. The site should also promptly communicate results to BMS. Participants meeting the criteria above may have potential DILI, see [Section 9.2.7](#) for reporting requirements.*

- For participants with elevated AST, ALT, or total bilirubin at Day 1 (Randomization), if there is a new elevation of ALT or AST  $> 2 \times$  baseline, or total bilirubin  $> 1.5 \times$  Day 1 total bilirubin (and to  $>$  ULN), repeat testing should be performed within 48 hours to 72 hours. If elevation persists, then study treatment will be discontinued if any of the following occur:

- ALT or AST levels increase to  $> 5 \times$  Day 1 (Randomization) measurement
- ALT or AST levels increase  $> 2 \times$  Day 1 (Randomization) measurements AND the increase is accompanied by a concomitant increase in total bilirubin to  $> 2 \times$  Day 1 bilirubin or the INR concomitantly increases by  $> 0.3$
- Appearance of fatigue, nausea, vomiting, right upper quadrant pain or tenderness, fever, rash, and/or eosinophilia ( $> 5\%$ )

*Note: If necessary, a local laboratory may be used for repeat testing, and results should be promptly communicated to the site. The site should also promptly communicate results to BMS. Participants meeting the criteria above may have potential DILI, see [Section 9.2.7](#) for reporting requirements.*

- Clinical signs of hepatic decompensation, including ascites, variceal bleeding, hepatic encephalopathy, or spontaneous bacterial peritonitis.
- Liver transplantation or planned liver transplant during the study.
- HCC.
- Any significant protocol violation (eg, demonstrated lack of treatment compliance). The violation should be discussed with the Medical Monitor prior to discontinuing the participant. Waivers for protocol violations will not be provided by the Sponsor or the Medical Monitor.
- The participant becomes pregnant (study treatment must be discontinued immediately). In the case of pregnancy ([Section 9.2.5](#)), the investigator must notify the Medical Monitor/designee of this event within 24 hours of awareness of the pregnancy. Follow-up information regarding the course of the pregnancy, including perinatal and neonatal outcome and, where applicable, offspring information must be reported on the Pregnancy Surveillance Form.
- Emergency unblinding performed by principal investigator.

See the SOA ([Section 2](#)) for details on the data to be collected at the time of treatment discontinuation and follow-up and any further evaluations that need to be completed.

Participants are not to be replaced. If study treatment is discontinued prior to the participant's completion of the study, the reason for the discontinuation must be documented in the participant's medical records and entered on the appropriate eCRF page. As indicated, appropriate follow-up and/or alternate medical care must be arranged for the participant.

Participants who discontinue study treatment before the Week 11 visit will have an ETT visit and will continue into the 24-week follow-up period. AEs and SAEs will be followed-up in line with [Section 9.2.3](#) and [APPENDIX 3](#).

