### 3) Prior and concomitant therapy

- a) Participants taking any OTC vitamin A-containing supplements or multivitamins, or vitamin A-containing medications after signing the ICF.
- b) Participants unable to comply with restrictions and prohibited treatments.
- c) **Not applicable per Revised Global Protocol v02** - Participants who have taken other investigational agents within 3 months prior to the liver biopsy used to confirm eligibility or within 12 weeks or 5 half-lives prior to the first dose of study treatment, whichever is longer.
- d) Prior exposure to BMS-986263.
- e) The participant has received recent treatment with alternative therapies, which, in the opinion of the investigator, could potentially confound clinical or laboratory assessments (eg, herbal supplements).
- f) Concomitant use of nintedanib is prohibited. Prior use of nintedanib is permitted but must be discontinued at least 3 days before the first dose of study treatment.
- g) **Not applicable per Protocol Amendment 03** - Participants who have received live attenuated vaccine or investigational SARS-CoV-2 vaccine within 3 months prior to the first dose of study treatment. Participants who have received a vaccine approved for Emergency Use Authorization by the United States (US) Food and Drug Administration (FDA) may be considered for inclusion, after discussion with the Medical Monitor.
- h) Participants who have taken other investigational agents except for investigational SARS-CoV-2 vaccine within 3 months prior to the liver biopsy used to confirm eligibility or within 12 weeks or 5 half-lives prior to the first dose of study treatment, whichever is longer.
- i) Participants taking any anticoagulants after signing the ICF.
- j) Participants who have received live attenuated vaccine or investigational SARS-CoV-2 vaccine within 3 months prior to the first dose of study treatment. Participants who have received a vaccine approved for Emergency Use Authorization by the United States (US) Food and Drug Administration (FDA) or other applicable country-specific regulatory agencies may be considered for inclusion.

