### 4) Physical and laboratory test findings

- a) Evidence of organ dysfunction or any clinically significant deviation from normal in physical examination, vital signs, ECG, or clinical laboratory determinations beyond what is consistent with the target population.
- b) The participant's baseline laboratory test results include abnormal values considered to be clinically significant by the investigator.
- c) **Not applicable per Revised Global Protocol v02** - The participant's laboratory test results at screening include any of the following:
  - Albumin  $< 3.5$  g/dL

- INR > 1.4 (participants who have an INR > 1.4 and who are taking an anticoagulant known to prolong INR may be included after discussion with the Medical Monitor)
- ALT value  $\geq 5 \times$  the ULN
- AST value  $\geq 5 \times$  the ULN
- Total bilirubin > 1.5 mg/dL, unless participant has a diagnosis of Gilbert Syndrome and direct bilirubin  $\leq$  ULN
- Platelet count < 140,000/ $\mu$ L
- Hemoglobin A1c  $\geq 9.0\%$
- Serum vitamin A (retinol) > ULN

d) Glomerular filtration rate < 30 mL/min/1.73 m^2 according to the Modification of Diet in Renal Disease equation at screening.

e) Centrally-read DXA scan BMD T-Score of -2.5 or less at the femoral neck, total hip, or lumbar spine during screening (in participants 40 years of age or older).

f) **Not applicable per Protocol Amendment 03** - The participant's laboratory test results at screening include any of the following:

- Albumin < 2.8 g/dL
- INR > 2.2
- ALT value  $\geq 5 \times$  the ULN
- AST value  $\geq 5 \times$  the ULN
- Total bilirubin > 3.0 mg/dL, unless participant has a diagnosis of Gilbert Syndrome and direct bilirubin  $\leq$  ULN
- Platelet count < 85,000/ $\mu$ L
- Hemoglobin A1c  $\geq 9.0\%$
- Serum vitamin A (retinol) > ULN

g) The participant's laboratory test results at screening include any of the following:

- Albumin < 2.8 g/dL
- International normalized ratio (INR) > 2.2
- ALT value  $\geq 5 \times$  the ULN
- AST value  $\geq 5 \times$  the ULN
- Total bilirubin > 3.0 mg/dL, unless participant has a documented diagnosis of Gilbert Syndrome, provided that total bilirubin is < 4.0 mg/dL and direct bilirubin is  $\leq$  ULN
- Platelet count < 85,000/ $\mu$ L
- Hemoglobin A1c  $\geq 9.5\%$
- Serum vitamin A (retinol) > ULN

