### **9.2.7      *Potential DILI***

Wherever possible, timely confirmation of initial liver-related laboratory abnormalities should occur prior to the reporting of a potential DILI event. The definition of potential DILI, as well as study treatment discontinuation criteria, are provided in [Section 8](#). All occurrences of potential DILIs, meeting the defined criteria, must be reported as SAEs (see [APPENDIX 3](#) for reporting details). Participants who meet criteria for potential DILI should have relevant laboratory testing (eg, ALT, AST, total bilirubin, and INR) repeated at least weekly until abnormalities have resolved or returned to baseline. Tests should be repeated within 3 days; then within every 3 days thereafter until reversal is noted; and thereafter, every week until normalization (or return to baseline). The investigator should make every effort to determine if any other cause for the liver test abnormalities is present.

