## SERIOUS ADVERSE EVENTS

SAE Definition is defined as any untoward medical occurrence that, at any dose:	
Results in death	Is life-threatening (defined as an event in which the participant was at risk of death at the time of the event; it does not refer to an event which hypothetically might have caused death if it were more severe)
	Requires inpatient hospitalization or causes prolongation of existing hospitalization (see note below)
	
NOTE: The following hospitalizations are not considered SAEs in BMS clinical studies:
 

• a visit to the emergency room or other hospital department < 24 hours, that does not result in admission (unless considered an important medical or life-threatening event)

• elective surgery, planned prior to signing consent

• admissions as per protocol for a planned medical/surgical procedure

• routine health assessment requiring admission for baseline/trending of health status (eg, routine colonoscopy)

• medical/surgical admission other than to remedy ill health and planned prior to entry into the study. Appropriate documentation is required in these cases

• admission encountered for another life circumstance that carries no bearing on health status and requires no medical/surgical intervention (eg, lack of housing, economic inadequacy, caregiver respite, family circumstances, administrative reason)

• admission for administration of anticancer therapy in the absence of any other SAEs (applies to oncology protocols)

Results in persistent or significant disability or permanent damage	
Is a congenital anomaly/birth defect	Is an important medical event (defined as a medical event(s) that may not be immediately life-threatening or result in death or hospitalization but, based upon appropriate medical and scientific judgment, may jeopardize the participant or may require intervention [eg, medical, surgical] to prevent one of the other serious outcomes listed in the definition above). Examples of such events include, but are not limited to, intensive treatment in an emergency room or at home for allergic bronchospasm; blood dyscrasias, or convulsions that do not result in hospitalization. Potential drug-induced liver injury (DILI) is also considered an important medical event (see Section 9.2.7 for the definition of potential DILI).

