**APPENDIX 5 CHILD-PUGH SCORING**

Parameter	Classification	Score
Bilirubin (Total) a	< 2 mg/dL (< 34.2 µmol/L)	+1
	2-3 mg/dL (34.2-51.3 µmol/L)	+2
	> 3 mg/dL (> 51.3 µmol/L)	+3
Albumin a	> 3.5 g/dL (> 35 g/L)	+1
	2.8-3.5 g/dL (28-35 g/L)	+2
	< 2.8 g/dL (< 28 g/L)	+3
International Normalized Ratio a	< 1.7	+1
	1.7-2.2	+2
	> 2.2	+3
Ascites	Absent	+1
	Slight	+2
	Moderate	+3
Encephalopathy	No encephalopathy	+1
	Mild to moderate (Grade 1-2)	+2
	Severe (Grade 3-4)	+3

a All laboratory parameters must be taken from the same blood draw.

Note: in the event of retesting of Child-Pugh Score, all laboratory parameters should be retested to allow for accurate calculations.

For the calculation of the Child-Pugh Score the sum of the scoring points from the 5 clinical parameters (total bilirubin, albumin, INR, ascites, and encephalopathy) corresponds to 1 of 3 categories:

Child-Pugh A = 5 to 6 points

Child-Pugh B = 7 to 9 points

Child-Pugh C =  $\geq$  10 points.

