## APPENDIX 6 FORMULAS FOR MEASUREMENTS

- Model for End-stage Liver Disease (MELD)  
Score =  $(9.57 * \ln[\text{creatinine}]) + (3.78 * \ln[\text{Bilirubin}]) + (11.20 * \ln[\text{INR}]) + 6.43$
- Enhanced liver fibrosis (ELF) assessment combines hyaluronic acid, procollagen 3 amino terminal peptide, and tissue inhibitor of metalloproteinase 1. An algorithm is used to evaluate each of these markers by immunoassay to create an ELF Score
- Fibrosis-4 (FIB-4) Score =  $(\text{age} [\text{years}] \times \text{aspartate aminotransferase [AST]} \text{ level} [\text{U/L}]) / (\text{platelet count} [\times 10^9/\text{L}] \times \text{square root of alanine aminotransferase [ALT]} [\text{U/L}])$
- Nonalcoholic fatty liver disease (NAFLD) Fibrosis Score =  $-1.675 + 0.037 \times \text{age} (\text{years}) + 0.094 \times \text{body mass index} (\text{kg}/\text{m}^2) + 1.13 \times \text{impaired fasting glucose/diabetes (yes = 1, no = 0)} + 0.99 \times \text{AST/ALT ratio} - 0.013 \times \text{platelet count} [\times 10^9/\text{L}] - 0.66 \times \text{albumin} (\text{g/dL})$
- AST-to-platelet ratio index (APRI) Score =  $([\text{AST} \text{ divided by AST Upper Limit of Normal}] / \text{platelet count} [\times 10^9/\text{L}]) \times 100$

Note: all laboratory parameters must be taken from the same blood draw. In the event of retesting, all laboratory parameters should be retested to allow for accurate calculations.

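### Section 8.1: a participant whose only raised Day 1 liver marker is INR falls under neither liver stopping rule, so the visible text gives no numeric ALT/AST stop and no potential-DILI definition

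*Combined protocol and SAP*

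**What the plan says.** Protocol Section 8.1 divides participants by Day 1 status and gives each group its own liver rule.

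- **First rule.** It begins "For participants with normal Day 1 (Randomization) liver enzymes, total bilirubin, and INR, if there is new elevation of ALT or AST" above 3 times ULN. The test is repeated in 48 to 72 hours. If the rise persists, drug stops at ALT or AST above 8 times ULN; above 5 times ULN for more than 2 weeks; above 3 times ULN with bilirubin above 2 times ULN or INR above 1.5; or above 3 times ULN with listed symptoms or eosinophilia.
- **Second rule.** It begins "For participants with elevated AST, ALT, or total bilirubin at Day 1 (Randomization), if there is a new elevation of ALT or AST" above twice baseline, and is also triggered by bilirubin above 1.5 times Day 1 and above ULN. After the same repeat test, drug stops at ALT or AST above 5 times Day 1; above 2 times Day 1 with bilirubin above 2 times Day 1 or an INR increase of more than 0.3; or with the listed symptoms or eosinophilia.

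A note under each rule ties its criteria to potential DILI. Section 9.2.7 says "The definition of potential DILI, as well as study treatment discontinuation criteria, are provided in" Section 8, and makes cases that meet those criteria reportable as SAEs. Appendix 3 says "Potential drug-induced liver injury (DILI) is also considered an important medical event" and points to Section 9.2.7 for the definition.

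On entry, Section 6.2 excludes "International normalized ratio (INR) > 2.2" under 4) g) and "Participants taking any anticoagulants after signing the ICF" under 3) i). It also excludes Child-Pugh above 6 and MELD above 14 (with a Gilbert Syndrome exception). Appendix 5 states "Child-Pugh A = 5 to 6 points". Section 9.1.2 provides for correcting a prolonged INR before biopsy, so raised INR is expected in this population.

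**The concern.** The entry conditions of the two rules are not complements. The first requires INR to be normal; the second leaves INR out of its list of abnormalities. Normal AST, ALT and bilirubin with a raised INR satisfies neither.

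Take two participants with the same normal Day 1 ALT and the same later, persistent rise to 9 times ULN. With a normal Day 1 INR, the rise is a mandatory stop and a potential DILI reported as an SAE. With a raised Day 1 INR, stopping rests on judgement and reporting on the general AE/SAE rules. Because anticoagulant users are excluded, a raised Day 1 INR should not be an anticoagulant effect, so in a cirrhosis trial the uncovered participant may be the one with less liver reserve. Section 3.3.1 itself names a theoretical liver risk from the DPD component.

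**Working it through.** There is no planned figure to reproduce here. The check has four steps: coverage of the rules, whether the uncovered group can be enrolled, where the definitions lead, and what each repair would do.

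**1. Coverage.** Classify AST, ALT, total bilirubin and INR as normal or raised on Day 1: 2 × 2 × 2 × 2 = 16 combinations.
- First rule: all four normal, 1 combination.
- Second rule: at least one of AST, ALT and bilirubin raised (2³ − 1 = 7), with either INR status: 7 × 2 = 14.
- Uncovered: 16 − 1 − 14 = 1, namely INR raised alone.

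The first rule speaks of liver enzymes without listing them, and Section 3.3.1 counts ALP among them. If ALP or GGT is added as a fifth marker there are 32 combinations. The second rule covers 7 × 4 = 28 and the first covers 1, leaving 3: INR alone, ALP/GGT alone, or both.

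**2. Can this participant be enrolled?** From Appendix 6, MELD = 9.57 ln(creatinine) + 3.78 ln(bilirubin) + 11.20 ln(INR) + 6.43. With creatinine and bilirubin both 1.0 mg/dL (assumed), the first two terms vanish:
- INR 1.3: 9.37
- INR 1.5: 10.97
- INR 1.7: 12.37
- INR 1.9: 13.62
- MELD of 14 is reached at INR = exp((14 − 6.43)/11.20) = 1.97

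Other assumed values move that ceiling. At creatinine 1.2 and bilirubin 1.0 it is 1.68. At creatinine 0.8 and bilirubin 0.8, INR 2.2 gives only 12.28, so the INR limit of 2.2 binds first. Child-Pugh, with albumin above 3.5 g/dL and no ascites or encephalopathy, is 5 for INR below 1.7 and 6 for 1.7 to 2.2. Both are allowed.

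**3. Where the definitions lead.** Appendix 3 refers to Section 9.2.7, which refers to Section 8, where the only visible criteria are those of the two rules. A participant outside both rules therefore has no criteria to meet.

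**4. What each repair would do.**
- *Add INR to the second rule.* It then covers 15 of the 16 combinations and the first rule covers 1.
- *Open the first rule to any INR.* It then covers 2 (INR normal or raised) and the second rule covers 14.

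Either way the total is 16 with no overlap. They differ in when they act. In multiples of ULN, for a normal Day 1 ALT:

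| Day 1 ALT | Second rule: repeat above (2 × Day 1) | Second rule: stand-alone stop above (5 × Day 1) | First rule: repeat above | First rule: immediate stand-alone stop above |
|---|---|---|---|---|
| 0.4 | 0.8 | 2.0 | 3 | 8 |
| 0.6 | 1.2 | 3.0 | 3 | 8 |
| 0.8 | 1.6 | 4.0 | 3 | 8 |
| 1.0 | 2.0 | 5.0 | 3 | 8 |

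The second rule's INR limb (increase above 0.3) suits this group as it stands. The first rule's limb (INR above 1.5) does not, because a Day 1 INR of 1.6 to 2.2 already exceeds it. Replacing it by Day 1 + 0.3 gives limits of 1.6, 1.8, 2.2 and 2.5 for Day 1 INR of 1.3, 1.5, 1.9 and 2.2.

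**The case against.** The best reply is that these participants are not unprotected. Section 8.1 requires drug to stop for any laboratory abnormality that the investigator judges to make continuation contrary to the participant's interest, and for clinical decompensation. It also has a stop for findings consistent with a blacked-out condition. Section 9 requires immediate discussion of safety concerns with the Medical Monitor. Section 9.2.6 captures clinically significant laboratory results, Section 9.2.7 asks for timely confirmation of liver abnormalities, Appendix 3 lets judgement make an event serious, and the DMC reviews safety. All of this stands, and it softens the harm. A reader might infer that the group has no stopping rule at all; the documents do not support that. But none of these provisions, as visible, gives an ALT or AST number, and the protocol did not consider judgement sufficient for everyone else.

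Text near the liver-monitoring passages is blacked out, so a numeric criterion there can be neither shown nor excluded. The point is limited to the visible text.

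A reader might also infer that this group should be kept out of the second rule because, with a low-normal ALT, it stops drug at 2 to 5 times ULN rather than 8. The documents do not support a prohibition. The second rule already takes participants with normal ALT and AST whose only abnormality is raised bilirubin. Its earlier repeat-test triggers, including one for bilirubin that the first rule lacks, may be wanted where liver reserve is reduced.

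Finally, Section 3.2.2 reports no potential DILI in earlier studies, and it is tempting to turn that into a ceiling on extra stops. Those studies were not selected for raised INR, their DILI definitions are not given, and two of them dosed for only 5 weeks. They do not supply such a ceiling.

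**Conclusion.** The coverage gap is certain on the visible wording. Of the 16 Day 1 combinations of AST, ALT, bilirubin and INR, exactly one is left out, and the eligibility limits admit it. That participant has no numeric ALT/AST stop, no 48 to 72 hour repeat-test trigger and no potential-DILI definition.

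How often this will matter is unknown. If 1%, 5% or 10% of the 270 randomised were affected (assumption), that would be about 3, 14 or 27 participants. The MELD figures rest on assumed creatinine and bilirubin values, and the eligibility limits apply at screening whereas the rules use Day 1. The consequence is uneven liver-safety handling and reporting, softened by the judgement-based provisions. It is worth correcting because a mandatory rule, followed literally, misses a group it should cover and the correction is cheap. Which correction is better is a clinical question that the documents do not settle.

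**What to change.** Make the two rules exhaustive by changing wording only, in one of two ways.

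1. **Add INR to the second rule**, so that its entry condition reads *elevated AST, ALT, total bilirubin, or INR at Day 1*. This matches how isolated raised bilirubin is already handled, and the existing INR-increase limb then applies unchanged. The drawback is earlier repeat tests and stops when Day 1 ALT is low-normal. Isolated raised ALP or GGT also stays open to interpretation unless *liver enzymes* in the first rule is changed to *AST, ALT*.
2. **Open the first rule**, so that it covers *normal Day 1 AST, ALT and total bilirubin, whatever the Day 1 INR*. Where Day 1 INR is above normal, use an INR increase of more than 0.3 from Day 1 in place of INR above 1.5. This also settles isolated raised ALP or GGT. The drawback is later triggers. There is also a small step in the INR limb: if the INR ULN is 1.1 (assumption), a Day 1 INR of 1.15 gives a limit of 1.45, slightly tighter than 1.5.

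The sponsor's hepatology advisers should choose. Both use thresholds already in Section 8.1.

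The cost is the Section 8.1 text, the laboratory-alert flags, occasional repeat tests and possibly a few extra early stops. No new scheduled sampling is needed: hematology (with INR) and chemistry are already drawn together on Days 1, 15, 29, 43, 57, 71 and 85. A stop before the Week 6 visit has no early-termination biopsy under Table 2 and so counts as a nonresponder under Section 10.4.1.
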